2 INTRODUCTION

2.1 Background & Rationale

Incontinence-Associated Dermatitis (IAD) is an inflammation of the skin that can occur when urine or feces come into contact with the perineal or perigenital skin.¹ The cause of IAD is incontinence of urine or bowel that results in a color change of the skin from pale to pink or deep red.² In addition, IAD is often associated with skin breakdown caused by pressure or shear.

According to the United States (US) Department of Human Services, the prevalence of a urinary and/or bowel incontinence among non-institutionalized persons aged 65 and over was 50.9%.³ Among institutionalized persons aged 65 and over, 39.0% reported urinary and/or bowel incontinence. Urinary incontinence was approximately two times more likely than bowel incontinence. Women were 1.2 times more likely to have urinary incontinence compared to men, while there was no difference in bowel incontinence. Also, there were no significant differences for incontinence among age, race, or educational background.³

In a similar study of 5342 acute care facility residents the prevalence rate of urinary and/or fecal incontinence was 45.7% and the overall IAD prevalence rate was 21.3% among the same acute care facility residents.⁴ In studies where prompted-voiding were encouraged, 30-66% percent of nursing home residents were able to reduce the episodes of incontinence to one episode per day.⁵ In addition, residents who achieved successful prompted urinary voiding during a 3-day trial period tended to maintain continence over a longer period of time.⁶

In an attempt to keep residents dry and make their urinary incontinence more manageable, caregivers place residents in absorbent incontinence products also known as adult briefs, which they check periodically for wetness and change when appropriate. Each resident is unnecessarily woken more than once per night only to discover that they don't need to be changed. This inefficient process of checking and changing the residents exists due to a lack of real-time data of residents' urinary patterns. This lack of data results in residents spending hours at a time in a wet brief increasing their risk of developing dermatitis, and pressure ulcers. Sleep is also compromised when caregivers wake up and check the residents during the night only to find that they are dry.

The use of adult disposable incontinence management products, primarily adult briefs (diapers) are used almost exclusively in this population due to decline in strength, intellect and physical ability. Those suffering from incontinence may lie in soiled diapers for prolonged periods of time resulting in indignity, discomfort, skin breakdowns and bedsores. But timely diaper change is needed to avert the problems of staying in soiled diapers. Ideally, caregivers must know who is incontinent and attend to those with soiled diaper without delays. But incontinence episodes can occur at any time; there is no fixed or regular timing. The current practice requires caregivers to check diaper wetness from one patient to another and to perform these scheduled diaper checks at every specified interval. This approach is time consuming, expensive, and labor intensive.

So it is not feasible and effective to provide around the clock care to multiple incontinent residents in nursing homes. Management of incontinence is an essential component of care provided in hospitals, long-term care homes, assisted living, retirement homes, private homes, and geriatric institutions. A key aspect of treating and preventing skin damage is to protect the skin from irritant exposure (such as urine). In order to minimize a resident's time spent in a filled brief, care providers may adhere to toileting schedules for each resident. Alternatively, they may adopt a "check-and-change" system

whereby residents' containment briefs are checked periodically for wetness when appropriate or convenient, and subsequently changed if wet.

In order to provide a desirable level of continence management, one solution is the use of a device that is designed to notify caregivers when incontinence episodes take place.⁷ There are products and devices available today, but none have been found to be a realistic, viable solution to aid caregivers with this daunting, time-consuming task of managing incontinence. In order to address this concern, we propose a solution using FitRight® System to aid caregivers of timely diaper changes. FitRight® System improves incontinence management by continuously monitoring incontinence episodes, empowering patient care staff in long-term care (LTC) settings with the data used to determine the appropriate continence care decisions.

The FitRight® System, aims to reduce or remove the "check" from check-and-change, using patent-pending technology to continuously monitor residents' briefs for wetness. The FitRight® System then wirelessly transmits this information to caregivers via a handheld device such as an iPod Touch. In doing so, the FitRight® System solution empowers caregivers to better manage their workflow while improving their residents' quality of life. The introduction of wearable technology into the set of tools used in incontinence management will reduce the time a resident is exposed to urine, thereby reducing the risk of associated (and costly) skin conditions. To institutions, this means indirect and direct cost savings and enhanced care compliance.

2.2 Study Product(s)

The investigational product being evaluated in this study is the FitRight® Connect™ Wetness Sensing System that includes the FitRight® Connect™ Pod, FitRight® Connect™ App, FitRight® Connect™ charger/adapter and FitRight® Connect™ Brief.

2.2.1. Product Overview:

The FitRight® Pod is a wearable sensor that monitors adult briefs for wetness and notifies caregivers when a resident becomes wet. In doing so, the FitRight® System may remove the need for caregivers to unnecessarily check residents while simultaneously ensuring residents are changed promptly as required. The FitRight® Pod is reusable and works by attaching to the outside of the FitRight® Brief. From the outside of the brief, the FitRight® Pod is able to monitor for and characterize moisture on the inside of the brief using a technique called impedance sensing.

The FitRight® Pod then transmits information wirelessly to a Wi-Fi enabled tablet. At a glance, caregivers can view the residents under their care, see who is wet and therefore requires immediate attention, and who is dry and shouldn't be disrupted.

2.2.2 Product Description:

The FitRight® System is used to help monitor and alert caregivers when it is appropriate to change the FitRight® Brief. The FitRight® System is composed of a wetness sensing brief, a pod that connects to Wi-Fi, and software that displays alerts on a display (FitRight® App). The FitRight® Brief is a wetness detection brief that is a non-sterile, disposable, single use device with a reusable wetness alert sensor (FitRight® Pod).

The FitRight® System alerts caregivers when a patient has micturated within the FitRight® Brief. An ink-based sensor is printed on the poly backsheet layer of the FitRight® Brief and when urine contacts the ink for a predetermined amount of time, it sends an alert to the FitRight® Pod that is attached on/secured to the outside of the FitRight® Brief. The FitRight® Pod translates that alert (via Wi-Fi) to the software application using a cloud-based server that is loaded on to a display device chosen by the user.

2.3 Risk/Benefit Profile

2.3.1 Potential Study Risks

This study entails minimal risk to the participants. The FitRight® System will be applied and operated according to the instructions for use (IFU). There is the possibility of minor skin irritation from the brief due to saline interaction, however, none is anticipated. In addition, the products will also be applied on the non-compromised skin of participants with no known skin conditions, which should impose less risk for study participants.

2.3.2 Potential Study Benefits

There may be no direct benefit to participants as a result of their participation in the study. The information gathered from this study may provide useful information to healthcare providers (HCP) on the efficacy of the FitRight® System. The knowledge gained as a result of this study may be used to identify novel approaches to improved incontinence care.

2.3.3 Assessment of Potential Risk/Benefit Profile

As this study entails minimal risk to the study participants and the results may identify novel approaches to improved incontinence care, the risk/benefit profile of this study is acceptable.

3 OBJECTIVES AND ENDPOINTS

OBJECTIVES	ENDPOINTS	JUSTIFICATION FOR ENDPOINT(S)

Primary Objective: To evaluate the FitRight® System sensor's ability to detect when an adult brief has absorbed enough liquid (~90-360 mL) normal saline via a simulated urinary void to trigger an alert to change the brief in the sitting, supine, and right or left side positions.
	
Primary Endpoint: The number of FitRight® System alerts when 90-360 mL normal saline has been absorbed into the brief in the sitting, supine, and right or left side positions.
	To determine the wetness/absorbency efficacy of the FitRight® Alert indicator in three positions

Secondary Objective: To determine the brief's residual volume capacity . In a subset of 22 participants, evaluate the FitRight® Brief after the brief has absorbed the maximum amount of liquid normal saline via a simulated
	
Secondary Endpoint: The weight of the filter paper after performing the rewet test with the FitRight® Brief after absorbing 360 mL of normal saline via a simulated void.
	To determine the brief's residual volume capacity for possible improvements to the FitRight® System.

OBJECTIVES	ENDPOINTS	JUSTIFICATION FOR ENDPOINT(S)
urinary void (360 mL) in the sitting position and then weighed via the rewet procedure.		

4 STUDY DESIGN

4.1 Overall Design

The purpose of this study is to validate the FitRight® Sensor's ability to detect when an adult brief has absorbed enough liquid (90-360 mL normal saline via simulated urinary void) to trigger an alert to change the brief. Data will be collected from healthy, normal, adult volunteers and will be used to assess the device's absorption and ability to trigger an alert.

Each participant will be provided with the FitRight® System for the duration of the investigation. Briefs will be used to collect real-life measurement data in order to validate the FitRight® System algorithms and the FitRight® Alert Indicator.

Each participant will be measured for the appropriately sized briefs using the participant's hip dimension and will wear this size throughout the study. Three sized briefs will be worn in three different positions (sitting, laying supine, and laying on either left or right side) in order to determine the efficacy of the FitRight® Alert Indicator. Participants will apply the briefs themselves and study staff will confirm correct application. Tubing will be setup in order to apply normal saline directly to the center of the brief.

Study staff will pour 90mL normal saline (first pour) to the brief via the tubing and will start a timer for five minutes. After five minutes, study staff will record whether the FitRight® Alert Indicator triggered an alert. Note: there is no minimum volume for the alert. If the alert does trigger, participant will remove the brief and apply the next brief for the next position. If the alert did not trigger, study staff will apply 150mL normal saline (second pour) and will start a timer for five minutes. After five minutes, study staff will record whether the FitRight® Alert Indicator triggered an alert. If the alert does trigger, participant will remove the brief and apply the next brief for the next position. If the alert did not trigger, study staff will apply 120mL normal saline (third pour) and will start a timer for five minutes.

After five minutes, study staff will record whether the FitRight® Alert Indicator triggered an alert. If the alert does trigger, participant will remove the brief and apply the next brief for the next position. If the alert did not trigger, study staff will apply 120mL normal saline (fourth pour) and will start a timer for five minutes. After five minutes, study staff will record whether the FitRight® Alert Indicator triggered an alert. Whether the FitRight® Alert Indicator triggered an alert or not, the participant will remove the brief and apply the next brief for the next position. Study staff will record whether the brief passed or failed to indicate. If the brief triggered an alert within the five minutes after the first, second, or third saline pour and prior to the fourth pour, the brief passed. If the brief did not trigger an alert by five minutes after the third pour, the brief fails. The fourth pour, if required, will help to determine if more volume was needed to trigger the alert or if the brief was defective.

The first 22 participants enrolled in the study will perform the rewet procedures. Participants will apply the sized brief and study staff will confirm correct application. Tubing will be setup in order to apply normal saline directly to the center of the brief. Study staff will pour 360 mL normal saline to the brief via the tubing and will start a timer for ten minutes. After ten minutes, participants will remove the brief and give the brief to the study staff. Study staff will weigh out at least 10.0 grams(g) filter paper (and as close to 10.0g as possible) and record the weight. Study staff will apply the filter paper centered on the wet brief and over the ADL layer, , apply a calibrated weight to the top of the filter paper, and start a timer for one minute. After one minute, the study staff will remove the calibrated weight and filter paper and weigh the wetted filter paper and record the weight. If any leakage or fluid infusion related issues occur during rewet testing this will be considered an invalid test (test failure) and this case will not be counted toward the 22 cases needed for rewet testing The data will still be recorded.

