8 STATISTICAL CONSIDERATIONS

8.1 Sample Size Determination

A sample size of 56 was chosen to evaluate the 95% confidence interval on the proportion of successful wetness alerts. The NCSS PASS procedure "Confidence Intervals for One Proportion" was used to solve for "CI width or distance from P to limit". It was assumed that the proportion of successes would be around 90% (0.85, 0.90 and 0.95 entered into PASS). Because testing will occur in 8 subgroups, the largest sample size that was a multiple of 8 that provided the most narrow 95% confidence limits was selected (N=56).

Rewet testing sample size: A convenient subset of the first 22 completed patients will be recruited for the rewet procedure. Patients will be considered complete if they have all data, for all three of the brief tests.

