8.9 Statistical Analysis

Statistical analyses will be conducted in SAS® software, Version 9.4 or higher of the SAS System for Windows (Copyright © 2013 SAS Institute Inc.) or other appropriate statistical software. P<0.05 will be considered statistically significant.

All continuous variables will be summarized using the following descriptive statistics: (non-missing sample size), mean, standard deviation, median, maximum and minimum. The frequency and percentages (based on the non-missing sample size) of observed levels will be reported for all categorical measures. 95% confidence intervals will be calculated for all means. In addition to summary statistics for the full sample and for each of the four positions with the key variable of interest being the percentage of tests that passed and those that failed for the full sample and for each of the four rotational positions will be calculated.

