8.9.1 Analysis of Primary Endpoints

The primary goal of this research study is to assess the reliability of the FitRight® Alert Indicator for the full sample and stratified by the four rotational positions, the three different fluid amounts,

and the combination of rotational positions and fluid amounts. Cronbach's coefficient alpha estimate's reliability by determining the internal consistency of a test or the average correlation of items within a test. The pass/fail values from this set of test runs will be compared to the derived variable of whether or not the test should have triggered an alert. Since the variables of interest are dichotomous (pass/fail), the coefficient alpha is equivalent to the Kuder-Richardson 20 (KR-20) reliability measure. It produces a correlation measure between 0 where a high KR20 coefficient (e.g., >0.90) is indicative of a homogeneous test. A reliability of 0.70 or higher for an acceptable rating and 0.80 or higher for a good rating.

In addition, a chi-square analysis will be conducted to determine if any association between rotational position and test status (pass/fail) exists. This analysis will be repeated to examine any possible associations between fluid added and test status (pass/fail).

Spearman correlation analysis will be used to examine possible associations between the key variables of triggered alert value (pass/fail), rotational position (sitting, supine, left side, right side), and fluid volume of 90 mL, 150 mL, 120 mL, and 120 mL with covariates of age, sex, and brief size. Additional t-tests or non-parametric tests will be employed to further examine any significant associations found in the correlational analyses between key and covariate measures.

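### The study is meant to validate the sensor, but no criterion is set on the proportion of briefs that alert, and the only stated benchmarks are on KR-20, which does not track that proportion

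*Combined protocol and SAP*

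**What the plan says.** - **Purpose.** Section 4.1: "The purpose of this study is to validate the FitRight® Sensor's ability to detect when an adult brief has absorbed enough liquid". Section 1.1 states the same purpose, and Section 4.1 uses *validate* again for the algorithms and the Alert Indicator.
- **Objective and endpoint.** The primary objective in Sections 1.1 and 3 is to *evaluate* the sensor. The primary endpoint is a count with no target: "The number of FitRight® System alerts when 90-360 mL normal saline has been absorbed into the brief".
- **Rule for one brief.** Section 4.1: "If the brief did not trigger an alert by five minutes after the third pour, the brief fails". Sections 1.2 and 6.4.2 agree.
- **Sample size.** Section 8.1: "A sample size of 56 was chosen to evaluate the 95% confidence interval on the proportion of successful wetness alerts". Success proportions of 0.85, 0.90 and 0.95 were entered to solve for interval width.
- **Summary of the rate.** Section 8.9 describes "the key variable of interest being the percentage of tests that passed and those that failed", for the full sample and by position. Section 8.5.3 adds stratification by volume. Section 8.9 promises 95% confidence intervals for means, while categorical measures get frequencies and percentages.
- **Benchmarks.** Section 8.9.1, on Cronbach's alpha (KR-20 for pass/fail data): "A reliability of 0.70 or higher for an acceptable rating and 0.80 or higher for a good rating". A value above 0.90 is described as showing a homogeneous test.

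**The concern.** A validation claim needs a rule that turns the observed alert proportion into a conclusion. The plan defines when one brief passes, but not how many of the 56 in a position must pass or whether every position must succeed. The values in Section 8.1 are planning assumptions for interval width. The P<0.05 in Section 8.9 is a general convention, and none of the tests specified in Section 8.9.1 compares the pass rate with a reference value.

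That leaves the KR-20 benchmarks as the only study-level numbers against which a result could be judged. KR-20 measures how consistently participants differ across items, not how often the sensor works. Used as the success mark, it could rate a poor sensor good and a good sensor unacceptable. The interval that justified the sample size, meanwhile, is not clearly among the planned outputs.

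**Working it through.** **1. The plan's own figure.** Inputs from Section 8.1: n = 56, p = 0.85, 0.90, 0.95, 95% confidence. The Wald half-width is 1.96 × √(p(1−p)/n). At p = 0.90 it is 1.96 × √(0.09/56) = 0.079; at 0.85 it is 0.094 and at 0.95 it is 0.057. The exact (Clopper-Pearson) width at p = 0.90 is 0.189 for n = 48, 0.174 for n = 56 and 0.162 for n = 64. No target width is stated and the width keeps falling as n grows, so N=56 can be neither reproduced nor refuted. It is a precision choice and implies no pass mark.

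**2. Does KR-20 track the pass rate?** KR-20 = k/(k−1) × (1 − Σp_j(1−p_j)/V), where p_j is the pass proportion for item j and V is the variance of the participant totals. Section 8.9.1 does not define the items; take the three positions, so k = 3.

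- *Fully concordant participants* (each passes all three or fails all three). Σp_j(1−p_j) = 3p(1−p) and V = 9p(1−p), so KR-20 = 1.5 × (1 − 1/3) = 1.0 for any p strictly between 0 and 1. That covers 50/56, 28/56 and 6/56. At 56/56 or 0/56, V = 0 and KR-20 is undefined.
- *Scattered failures.* Let 17 participants fail once each, split 6, 6 and 5 over the positions, so 151/168 = 89.9% of briefs pass. Σp_j(1−p_j) = 2 × (50/56)(6/56) + (51/56)(5/56) = 0.2726. V = (17/56)(39/56) = 0.2114. KR-20 = 1.5 × (1 − 0.2726/0.2114) = −0.43.
- *Independent failures at a true 90%.* In 2,000 simulated studies the mean was about −0.03 and none reached 0.70.
- *Result paired with the derived variable of Section 8.7.* That variable is 1 once 90 mL has been added, and the first pour is 90 mL, so it is constant. With k = 2 and one constant item, V = p(1−p) and KR-20 = 2 × (1 − 1) = 0.

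**3. What the pass proportion would show.** Exact 95% limits are the 0.025 quantile of Beta(x, n−x+1) and the 0.975 quantile of Beta(x+1, n−x), with n = 56:

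| Pass | Proportion | Exact 95% CI |
|---|---|---|
| 28 | 50.0% | 36.3–63.7% |
| 42 | 75.0% | 61.6–85.6% |
| 50 | 89.3% | 78.1–96.0% |
| 56 | 100% | 93.6–100% |

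The plan attaches no different conclusion to any of these rows.

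**4. What a criterion would imply.** The documents give no acceptance limit, so the marks below are assumed for illustration. The rule is that the exact lower limit is at least the mark. Entries are P(X ≥ count) for X ~ Binomial(56, p), in one position:

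| Mark | Count needed | p = 0.85 | p = 0.90 | p = 0.95 |
|---|---|---|---|---|
| 75% | 49/56 | 0.383 | 0.807 | 0.994 |
| 80% | 51/56 | 0.136 | 0.507 | 0.940 |
| 85% | 53/56 | 0.024 | 0.176 | 0.693 |

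If positions are independent, the chance that all three meet the 75% mark is 0.807³, about 0.52, at a true 90%, and 0.994³ = 0.98 at a true 95%.

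**The case against.** The best reply is that this is an estimation study. The formal objective says *evaluate*, the endpoint is a count, Section 8.9.1 speaks of assessing reliability, and the sample size rests on interval width. An estimation study needs no pass mark. This largely stands, and it is why a change of wording is an acceptable remedy. It does not account for *validate* in Sections 1.1 and 4.1, or for the benchmarks being placed on KR-20.

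A second reply is that the mean of a 0/1 variable is a proportion, so an interval for means could cover the pass rate. That reading is possible, but Section 8.9 treats categorical measures separately and gives them only frequencies and percentages. The interval should be stated.

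A reader might go further and infer that any observed rate can be reported as validation, or that a weak position could be averaged away. The documents do not support either. They commit the sponsor to no binary claim, and percentages by position are prespecified, so 42/56 and 56/56 would appear as visibly different results and a weak position would show.

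It is also fair to say that the marks in the last table have no source in the plan. The spread of probabilities there shows what a choice of mark entails and is not a measured bias.

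**Conclusion.** The point holds in this form: the purpose and the objective use different verbs, no study-level criterion is set on the alert proportion, and the only numerical benchmarks are on a coefficient that does not follow that proportion. KR-20 can be 1.0 with 6 of 56 participants passing, and −0.43 with 89.9% of briefs passing. The interval for which N=56 was chosen is not expressly planned.

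The KR-20 results assume that positions are the items; pairing the result with the constant derived variable gives 0 instead. The binomial figures use one brief per participant within a position. The all-positions figures assume independence, although the same participants supply all three.

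The data would remain usable. What is undefined is the conclusion to be drawn from them, so this should be settled before pass/fail results are reviewed.

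**What to change.** In Section 8.9.1, make the primary result the brief-level pass proportion (alert by five minutes after the third pour) with an exact two-sided 95% confidence interval in each of sitting, supine and side-lying (left and right combined), n = 56 each. State that KR-20 is not the success mark. Then choose one of two routes:

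- **(a) Keep the validation claim.** Before pass/fail data are reviewed, state a lower-limit criterion that the sponsor justifies, give its required count, and say that every position must meet it. For illustration, 75% needs 49/56, 80% needs 51/56 and 85% needs 53/56. The 75% figure is a placeholder, not a recommendation. Because all positions must succeed, no multiplicity adjustment is needed.
- **(b) Drop the claim.** Replace *validate* with *estimate* in Section 1.1 and at both places in Section 4.1, and say that the study makes no validation claim.

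Either route costs a few sentences and needs no new participants, procedures or data. Under (a) the sponsor is bound to a mark it could miss: even at 75%, a true 90% sensor meets it in all three positions only about 52% of the time under independence. Under (b) it gives up the word *validated*.
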